5.6.2. Analysis of Secondary Efficacy Variables

The secondary efficacy endpoints will be analyzed using an ANCOVA model in the same fashion as the primary analysis of the primary endpoint.

Average Daily Symptom Score Endpoints (TOSS, TNSS, DMS, TSS)

The average TOSS, TNSS, and DMS will be calculated using all observed daily scores during the specified time period (initial 12 weeks or last 12 weeks of the treatment period).

The average TSS will be calculated by adding average TNSS and average TOSS during the specified time period (initial 12 weeks or the last 12 weeks of the study).

The intercurrent events, strategies, and the corresponding missing data handling approaches for these endpoints will follow the same strategy as for the primary endpoint, outlined in [Table 4](#).

Supplemental analyses using non-parametric methods, such as Wilcoxon ranked sum test or Hodges-Lehmann analysis of median differences, may be performed in the event of a violation of the normality assumption.

Asthma-related endpoints (ADSS, FEV1, ACQ-5)

All asthma endpoints will be analyzed on patients in the FAS with asthma (all randomized patients with ongoing asthma in medical history). Supplemental analyses may be performed in the subset of ongoing asthma patients who were also on asthma medication at baseline.

All available daily ADSS will be averaged over the specified time period (initial 12 weeks or last 12 weeks of the treatment period). If ADSD or ANSD is missing on any given day, ADSS score for that day will be considered missing and no value will be calculated. In addition, ANSD will be shifted by one day, i.e., ADSD on Day 1 and ANSD on Day 2 will be used to get the ADSS on Day 1, ADSD on Day 2 and ANSD on Day 3 will be used to get the ADSS on Day 2, and so on. The day before Visit 6 or Visit 14 for the initial 12 weeks and last 12 weeks, respectively, will be the last day that contributes to the average ADSS (since there will generally be no ANSD measurement corresponding to the date of Visit 6 or 14).

The estimand for ADSS will follow the same approach as for the primary endpoint, described in [Table 4](#). Separate analyses of average ADSD and average ANSD may also be performed.

Estimands for FEV1 and ACQ-5 are specified in [Table 5](#). A supplemental analysis may be performed for the change from baseline ACQ-5 endpoint only in patients with baseline ACQ-5 > 1.5.

Supplemental analyses using non-parametric methods, such as Wilcoxon ranked sum test or Hodges-Lehmann analysis of median differences, may be performed in the event of a violation of the normality assumption.

Prohibited medications and corresponding data utilization methods relevant for asthma endpoints are specified in [Table 8](#)

SPT endpoints

The intercurrent events, strategies, and the corresponding missing data handling approaches for the SPT endpoints are outlined in [Table 5](#).

Prohibited medications and corresponding data utilization methods relevant for SPT endpoints are specified in [Table 9](#)

Table 5: Summary of Estimands for Secondary Endpoints of Clinical Importance

Endpoint Category	Estimands			
	Endpoint(s)	Population	Intercurrent event(s) handling strategy and missing data handling	Population-level summary
Secondary endpoint – Continuous, SPT, and RQLQ(S)+12	Percent change from baseline to week 12 and end of treatment (week 60) cat SPT mean wheal diameter Change from baseline to week 60 in RQLQ(S)+12	FAS	
The intercurrent events will be handled as follows⁵:
 
 1. Discontinuing the study intervention: all data collected after discontinuation will be used in the analysis (treatment policy strategy) 2. Rescue treatment¹ and select prohibited medications^{2,4} to treat allergic symptoms during the efficacy assessment period: data after allergy-relieving rescue medication will be used in the analysis (treatment policy strategy) 3. Prohibited medications taken during the protocol defined window leading up to the relevant visit (week 12 or week 60) which are adjudicated to be handled using a composite strategy⁴: data will be set to missing and imputed using the worst value of all observations in corresponding treatment group. 	
ANCOVA model with treatment group, stratification factors, and cat sIgE (<17.5 kUa/L versus \geq17.5 kUa/L) as fixed factors and relevant baseline measurement as a covariate.
 
LS-means estimates will be provided for each treatment group, as well as the difference between REGN1908-1909 and placebo with corresponding 95% confidence interval and 2-sided p-value.

Secondary endpoint – Continuous, FEV1, and ACQ-5	Percent change from baseline to week 12, week 60 FEV1 Change from baseline to week 60 in ACQ-5	FAS with asthma	
 4. Prohibited taken during the protocol defined window leading up to the relevant visit (week 12 or week 60) which are adjudicated to be handled using a hypothetical strategy^{3,4}: data will be set to missing and multiple imputation will be used. 5. Patient does not have exposure to cat leading up to assessment⁶: 
 a. If no cat is living in the patient's home leading up to assessment: all available data will be used in analysis (treatment policy) b. If patient is traveling away from home for less than 42 consecutive days prior to the assessment: all available data will be used in the analysis (treatment policy); otherwise (for travel \geq42 consecutive days), data will set to missing and multiple imputation will be used (hypothetical strategy) 	

Endpoint Category	Estimands			
	Endpoint(s)	Population	Intercurrent event(s) handling strategy and missing data handling	Population-level summary
			
In addition, if a patient has no available value of the relevant measurement at the specified visit, the imputation rules are as follows:
 
 • Missing data because of patients' discontinuation from study due to AEs and lack of efficacy will be imputed using worst score of all the observations in corresponding treatment group • Missing data due to any other reason will be imputed using MI. 	

[1] Note that for SPT endpoints, oral antihistamines are considered as prohibited medication, as specified in [Table 9](#)

[2] Category 1 of [Table 7](#) (RQLQ), [Table 8](#) (asthma), [Table 9](#) (SPT) lists prohibited medications that will be handled using a treatment policy

[3] Additional prohibited medications listed in Category 2 of [Table 7](#), [Table 8](#), and [Table 9](#) will undergo blinded adjudication by study medical monitor before the database lock to determine they will be handled by treatment policy, composite strategy, or hypothetical strategy

[4] Prohibited medications that are not indicative of treatment failure and will be handled by hypothetical strategy are defined in Category 3 of [Table 8](#) and [Table 9](#)

[5] If a data point or missing value falls into multiple categories of intercurrent events as specified above, the following priority order for handling of data will be applied: ICE 3), ICE 4), ICE 5b), ICE 5a), ICE 1), ICE 2). For example, if data or missing value fall into both ICE 3) and 4), the strategy for ICE 3) should be followed, as it takes priority over ICE 4).

[6] This intercurrent event is not relevant for the SPT endpoints

5.6.3. Adjustment for Multiple Comparisons

A non-binding futility interim analysis (IA) is planned in this study (details are provided in Section 7) and an administrative penalty of 0.001 will be taken from the significance level used at final analysis, and thus 2-sided 0.049 will be used. No further multiplicity adjustment will be performed for the IA.

The following multiplicity adjustment approach, a hierarchical procedure, will be used to control the overall Type-1 error rate at 0.049 for the primary endpoint and the secondary endpoints of R1908-1909 versus placebo. Each hypothesis will be formally tested only if the preceding one is significant at the 2-sided 0.049 significance level. The hierarchical testing order is shown in below table (all comparisons are with the placebo).

Level	Endpoints	Testing Order
Primary endpoint	Daily CSMS, averaged over the last 12 weeks of the treatment period (weeks 48 to 60)	1
Secondary endpoints	Daily TNSS, averaged over the last 12 weeks of treatment period (weeks 48 to 60)	2
	Percent change from baseline to the end of treatment (week 60) in cat SPT mean wheal diameter	3
	Percent change from pre-treatment baseline in average TNSS, over the last 12 weeks of the treatment period (weeks 48 to 60)	4
	Daily CSMS, averaged over the initial 12 weeks of the treatment period (weeks 0 to 12)	5
	Daily TNSS, averaged over the initial 12 weeks of treatment period (weeks 0 to 12)	6
	Daily TSS, averaged over the last 12 weeks of the treatment period (weeks 48 to 60)	7
	Daily TSS, averaged over the initial 12 weeks of the treatment period (weeks 0 to 12)	8
	Percent change from pre-treatment baseline in average CSMS, over the last 12 weeks of the treatment period (weeks 48 to 60)	9
	Change from baseline to week 60 in RQLQ(S)+12	10
	DMS, averaged over the last 12 weeks of the treatment period (weeks 48 to 60)	11
	Daily TOSS, averaged over the last 12 weeks of the treatment period (weeks 48 to 60)	12
	Percent change from pre-treatment baseline in average TSS, over the last 12 weeks of the treatment period (weeks 48 to 60)	13

5.6.4. Subgroup analysis

Subgroups defined in Section 3.5 for the primary endpoint will be analyzed based on the FAS.

The analysis method for the subgroups will be the same as the primary analysis described in Section 5.6.1, as appropriate. If for any reason, such as small number of patients in a subgroup, the model-based inferential statistics cannot be computed, or deemed inappropriate, only descriptive statistics will be provided.

Forest plots of the primary efficacy endpoint across subgroups will be provided.

5.6.5. Analysis of Exploratory Efficacy Variables

For continuous exploratory efficacy variables, e.g., percent change in ADSS, they will be analyzed by using an ANCOVA model similar to the analyses of primary endpoint.

5.7. Analysis of Safety Data

The analysis of safety will be performed on the SAF, as defined in Section [3.2](#).

The safety analysis will be based on the reported AEs and other safety information (clinical laboratory evaluations, and vital signs).

Thresholds for treatment-emergent Potential Clinically Significant Values (PCSV) in laboratory variables and vital signs are defined in Section [10.3](#). Treatment-emergent PCSV is any PCSV that developed or worsened in severity compared to the baseline during the on-treatment and follow-up period. The baseline when determining treatment-emergent PCSV refers to the baseline value of the study.

The summary of safety results will be presented for each treatment group. The time interval to detect any event or abnormality is between the first injection of study medication and EOS.

In addition, the summary of safety results (including TEAEs, clinical laboratory, vital signs, and ECG) will be performed for subjects who were impacted by COVID-19 pandemic and not impacted by COVID-19 pandemic in each study part, respectively if deemed appropriate. The summary will be performed for pre-, during, and post-COVID-19 periods for patients impacted by COVID-19, if deemed appropriate.

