## 11.4.6. Safety Analysis

The analysis population for the safety endpoints (SAF) includes all randomized patients who receive at least 1 injection of study drug and will be analyzed according to the intervention they actually received. The SAF will be the basis for the analyses for the study period. The safety analyses will be based on descriptive statistics using the observed data. The number and percentage of patients with at least 1 treatment-emergent adverse event (TEAE), treatment-emergent SAE, treatment-emergent AESI, treatment-related TEAE, and TEAE leading to treatment discontinuation will be tabulated by treatment group. Descriptive statistics of values and change from baseline values for each laboratory and vital signs parameters will be summarized by treatment group at each time point. The number and percentage of patients with at least 1 incidence of potentially clinically significant abnormality at any time during the treatment-emergent period will be summarized by treatment group.

The SAP for the study will be developed and finalized before database lock. Statistical analyses were conducted with SAS software version 9.4 or above.

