#### Laboratory Tests

Laboratory test results will be summarized by baseline and change from baseline to each scheduled assessment time with descriptive statistics.

Number and percentage of patients with a potentially clinically significant value (PCSV) at any post randomization time point will be summarized for each clinical laboratory test for all patients and separately for patients in whom the PCSV criterion was normal or missing at baseline.

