5.7.2. Clinical Laboratory Measurements

Laboratory measurements include clinical chemistry, hematology, and urinalysis results, and will be converted to standard international units and US conventional units. Summaries of laboratory variables will include:

- Descriptive statistics of laboratory result and change from baseline by visit
- The number (n) and percentage (%) of subjects with treatment emergent PCSVs. This summary will be provided based on all patients in the SAF as well as in the subgroup of SAF, patients who did not meet the PCSV criterion at baseline.
- Shift tables based on baseline normal/abnormal and other tabular and graphical methods may be used to present the results for parameters of interest

The graph of mean change and/or percent change from baseline value for lab parameters by visit will be provided.

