Monocytes	>0.7 Giga/L and ≤ 0.7 Giga/L at baseline		>1.2 Giga/L and ≤ 1.2 Giga/L at baseline		>0.7 [>1.2] Giga/L ≤ 0.7 [≤ 1.2] Giga/L at baseline

Parameter	Adults	Comments for adults	Adolescents (≥ 12 to < 18)	Comments for adolescents	Combined
Basophils	>0.1 Giga/L and ≤ 0.1 Giga/L at baseline		>0.2 Giga/L		>0.1 Giga/L and ≤ 0.1 Giga/L at baseline [>0.2 Giga/L]
Eosinophils	(>0.5 Giga/L and $>$ ULN) and (≤ 0.5 Giga/L or \leq ULN at baseline)	Harrison- Principles of Internal Medicine 17th Ed., 2008.	(>0.5 Giga/L and $>$ ULN) and (≤ 0.5 Giga/L or \leq ULN at baseline)	Harrison- Principles of internal Medicine 17th Ed., 2008.	(>0.5 Giga/L and $>$ ULN) and (≤ 0.5 Giga/L or \leq ULN at baseline)
Hemoglobin	≤ 115 g/L and > 115 g/L at baseline for male; ≤ 95 g/L and > 95 g/L at baseline for Female. ≥ 185 g/L and < 185 g/L at baseline for Male; ≥ 165 g/L and < 165 g/L at baseline for Female Decrease from Baseline ≥ 20 g/L	Three criteria are independent. *The default criteria. By gender (male and female) are optional. Criteria based upon decrease from baseline are more relevant than based on absolute value. Other categories for decrease from baseline can be used (≥ 30 g/L, ≥ 40 g/L, ≥ 50 g/L).	<100 g/L and ≥ 100 g/L at baseline (or <10 g/dL and >10 g/dL at baseline) ≥ 200 g/L and <200 g/L at baseline (or ≥ 20 g/dL and <20 g/dL at baseline) Decrease from Baseline ≥ 20 g/L	Two criteria are independent	≤ 115 g/L and > 115 g/L at baseline for male; ≤ 95 g/L and > 95 g/L at baseline for Female. [<100 g/L and ≥ 100 g/L at baseline] ≥ 185 g/L and < 185 g/L at baseline for Male; ≥ 165 g/L and < 165 g/L at baseline for Female [≥ 200 g/L and <200 g/L at baseline] Decrease from Baseline ≥ 20 g/L
Hematocrit	≤ 0.37 v/v and > 0.37 v/v at baseline for Male ; ≤ 0.32 v/v and > 0.32 v/v at baseline for Female ≥ 0.55 v/v and < 0.55 v/v at baseline for Male ; ≥ 0.5 v/v and < 0.5 v/v at baseline for Female	Two Criteria are independent *The default criteria. By gender (male and female) are optional.	<0.37 v/v and ≥ 0.37 v/v at baseline for Male ; <0.33 v/v and ≥ 0.33 v/v at baseline for Female >0.52 v/v and ≤ 0.52 v/v at baseline for Male ; >0.47 v/v and ≤ 0.47 v/v at baseline for Female	Two criteria are independent	≤ 0.37 [<0.37] v/v and > 0.37 [≥ 0.37] v/v at baseline for Male ; ≤ 0.32 [<0.33] v/v and > 0.32 [≥ 0.33] v/v at baseline for Female ≥ 0.55 [>0.52] v/v and < 0.55 [≤ 0.52] v/v at baseline for Male ; ≥ 0.5 [>0.47] v/v and < 0.5 [≤ 0.47] v/v at baseline for Female

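### For single-threshold laboratory tests, the baseline clause in SAP 10.3 makes the two PCSV tables in SAP 5.7.2 count the same patients, so worsening from beyond a cut-off is missed

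*SAP*

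**What the plan says.** Three places set the counting rule for laboratory PCSVs.

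- **Protocol 11.4.6.2 (Laboratory Tests)** counts a "potentially clinically significant value (PCSV) at any post randomization time point" and tabulates it "for all patients and separately for patients in whom the PCSV criterion was normal or missing at baseline". The all-patient table carries no baseline condition. Protocol 11.4.6 words it slightly differently: "at least 1 incidence of potentially clinically significant abnormality at any time during the treatment-emergent period".
- **SAP 5.7** states: "Treatment-emergent PCSV is any PCSV that developed or worsened in severity compared to the baseline during the on-treatment and follow-up period". It then points to the operational list: "Thresholds for treatment-emergent Potential Clinically Significant Values (PCSV) in laboratory variables and vital signs are defined in Section" 10.3.
- **SAP 10.3** adds to almost every chemistry and hematology criterion that the same cut-off was not met at baseline. Adult alkaline phosphatase, for example, must exceed 1.5 x ULN after a baseline at or below 1.5 x ULN.

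SAP 5.7.2 tabulates treatment-emergent PCSVs twice, the second time only in patients whose baseline value did not reach the threshold: "This summary will be provided based on all patients in the SAF as well as in the subgroup of SAF, patients who did not meet". SAP 6.4 counts a post-baseline PCSV with a missing baseline as treatment-emergent. SAP 1.2.4, which lists departures from the protocol's statistical section, does not mention PCSVs.

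**The concern.** Two tables are useful when they differ: one shows how many patients had a significant value at all, the other how many acquired one. If the event definition already excludes everyone past the cut-off at baseline, the first table repeats the counts of the second over a larger denominator and adds no information. The patients it could have shown, those who start beyond a cut-off and move further, are in neither table, although SAP 5.7 says worsening counts and the protocol's all-patient table would include them. At stake is the visibility of a laboratory safety signal in patients with an abnormal baseline.

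**Working it through.** The documents give no figure to reproduce, so the check classifies the criteria and then applies the three rules to the same cases.

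**Step 1: classify the laboratory criteria in SAP 10.3.** Low and high limits are counted separately; race and sex variants are counted once.

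| | Adults | Adolescents |
|---|---|---|
| Rows with a criterion | 23 | 23 |
| Criteria | 44 | 44 |
| With a same-cut-off baseline clause | 41 | 41 |
| Change-from-baseline criteria | 3 (creatinine 2, hemoglobin 1) | 2 (creatinine 1, hemoglobin 1) |
| No baseline clause | 0 | 1 (basophils) |

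In adults, 41/44 = 93% of criteria carry the clause. Five rows can still register worsening: ALT, AST and bilirubin through their upper tiers, creatinine and hemoglobin through change criteria. That leaves 23 - 5 = 18 rows that cannot. One of these is uric acid, which is not in the chemistry panel of SAP 4.6.3. Without it the count is 17 of 22.

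**Step 2: apply the rules to one single-threshold test.** Take adult alkaline phosphatase on a hypothetical grid, in multiples of ULN: baseline missing, 1.0, 1.4, 2.0 or 3.0; worst post-baseline 1.0, 2.0 or 4.0. That gives 5 x 3 = 15 patterns.

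- SAP 10.3 with SAP 6.4 (post above 1.5, baseline at or below 1.5 or missing): 3 x 2 = **6**.
- SAP 5.7, reading a further rise as worsened: the same 6 plus 2.0 to 4.0 and 3.0 to 4.0 = **8**.
- Protocol 11.4.6.2 (any post-baseline value above 1.5): 5 x 2 = **10**. The last two are 2.0 to 2.0 and 3.0 to 2.0, which are stable or improving.

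**Step 3: compare the two SAP tables on this grid.** With known baselines only, the all-patient table gives 4 of 12 and the not-met-at-baseline table 4 of 6: same numerator, different denominator. With missing baselines in both tables, the counts are 6 of 15 and 6 of 9. If missing baselines are kept out of the second table, its count is 4 of 6 against 6 of 15. SAP 5.7.2 does not say which applies; the protocol puts them in.

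**Step 4: check a tiered test.** For ALT, a move from 4 to 6 x ULN is counted in the tier above 5 and up to 10, and a move from 6 to 12 in the tier above 10 and up to 20. Moves from 4 to 4.9 and from 6 to 9 stay within a tier and are not counted. Upper tiers therefore capture worsening that crosses a tier boundary.

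**The case against.** The strongest reply is that SAP 5.7 and SAP 10.3 can be read together: a PCSV worsens in severity by moving to a higher tier, and a test with one threshold has no higher tier. On that reading nothing is lost that was promised. It does reconcile the two SAP sections, but it leaves the redundant table and the difference from Protocol 11.4.6.2.

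It can also be said that emergent cases over all treated patients is a legitimate incidence, computed alike in both arms. That stands: the point concerns redundancy and visibility, not bias between arms. SAP 5.7.2 also commits to change-from-baseline statistics and mean-change graphs, and investigators report abnormalities as adverse events under Protocol 10.1.1. A marked individual rise is thus not invisible, but means do not show individual worsening, and shift tables are only optional.

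Three stronger readings are tempting and are not supported:

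- **That a normal baseline is required.** The clause is only that the same cut-off was not met. ALT of 2.9 x ULN is abnormal and passes.
- **That all worsening goes uncounted.** The upper ALT and AST tiers, the upper adult bilirubin tier, and the creatinine and hemoglobin change criteria do register it.
- **That eosinophils make the omission large in an allergic population.** That criterion needs a value above 0.5 Giga/L and above ULN, and a baseline at or below either limit still qualifies. A patient at 0.6 Giga/L at baseline remains countable if ULN is 0.6 or higher. The documents give neither the ULN nor a baseline distribution, so no share can be derived.

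Screening also limits the problem. Before dosing, the Schedule of Events has hematology and chemistry only at screening. Footnote 4 requires screening safety assessments to be normal before study drug, and exclusion criterion 7 removes clinically significant deviations as judged by the investigator, naming low platelets and neutrophils. Investigator judgement leaves room for some abnormal baselines, but probably few.

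**Conclusion.** The point holds as a minor inconsistency in safety reporting. Protocol 11.4.6.2, SAP 5.7 and SAP 10.3 give different counting rules, and SAP 1.2.4 does not declare the difference. For about 18 of 23 adult rows, the two tables in SAP 5.7.2 share a numerator when baseline is known, and a patient past the cut-off at baseline who worsens is in neither. The exceptions are the upper ALT, AST and adult bilirubin tiers, the creatinine and hemoglobin change criteria, adolescent basophils and missing baselines. The row count depends on the conventions in Step 1, and the grid illustrates the logic without estimating a rate. The number of patients affected cannot be obtained from the documents and is probably small.

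**What to change.** In SAP 5.7.2 and 10.3:

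1. Apply the baseline clause only to the table of patients who did not meet the criterion at baseline, adolescent basophils included. State that missing baselines belong in that table, as in the protocol.
2. Make the all-SAF table any post-baseline PCSV, as Protocol 11.4.6.2 says. Do not label it treatment-emergent, because it will also count patients who were stable or improving, such as alkaline phosphatase going from 3.0 to 2.0 x ULN.
3. Add a listing of baseline and worst post-baseline values for patients past the cut-off at baseline. This is what makes worsening visible; the all-SAF table alone cannot separate it from persistence.

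The cost is SAP wording, one programming flag and one listing, settled before database lock. The all-SAF percentages will rise, possibly more than slightly, because they then include pre-existing abnormalities, and the table should carry a note saying so.
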